The Community United to Challenge Asthma - Project CURA (Clinical Trials ID NCT01065883 and NCT01061424) was a behavioral randomized controlled trial to test the efficacy of a CHW intervention to improve medication adherence and reduce home triggers among Puerto Rican children and adolescents.¹⁰⁻¹² Fifty-one children in elementary school and 50 children in high school were recruited and randomized to receive either CHW home visits or mailed information. Both interventions lasted four months and covered a standard asthma core curriculum emphasizing physiology, triggers, medications, and physician communication. The interventions also included information on self-management skills. Data were collected at the end of the intervention period and one-year from the start date to assess maintenance. The sample was intentionally poorly controlled at baseline; all met criteria for either uncontrolled and/or persistent asthma over the past year. Only 45% of the Elementary School Cohort and 12% of the High School Cohort had an inhaled corticosteroid at baseline. For those with an inhaled corticosteroid, the combined median adherence was 1.0 doses/day (range 0-3.3), meaning about 25% adherent to standard metered dose inhaler regimens. Homes had an average of six asthma triggers. Prevalence of depression was very high: 59% of caregivers and 68% of teens reported signs of depression. In the Elementary School Cohort (n=51), no differences were seen in outcomes between arms at any time point with one exception: the CHW arm had lower odds of having an ICS (OR=0.2; p=0.02) at 12-months. Every point increase in baseline caregiver depressive symptoms was associated with a lower odds of controlled asthma (OR 0.9; 95% CI = 0.8, 1.0; p=0.02). The only significant treatment arm difference in the High School Cohort (n=50) was in inhaler technique. At 5-months, the CHW arm performed 18.0% (95% CI = 8.0, 28.1; p <0.01) more steps correct than the Mailings arm. At 12-months, the CHW arm performed 14.2% (95% CI = 4.4, 24.1; p <0.01) more steps correct than the Mailings arm.

The Community United to Raise Awareness: Asthma and Active Living: CURA 2 (1P50HL105189-01) was a follow-up to Project CURA where the number of CHW visits was

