3.0 Objectives/Aims

Primary Aim 1: To assess the efficacy of the integrated CHW home asthma intervention, relative to clinic-based AE-C education over 12-months, as demonstrated by asthma control. We hypothesize that the CHW arm will have significantly greater asthma control than the AE-C arm at 12-months as measured by days with activity limitation over the previous 14 days and the Asthma Control Test/childhood Asthma Control Test.

Specific Aim 2: To assess maintenance of intervention efficacy, as demonstrated by asthma control at 18 and 24 months after randomization. We hypothesize that changes in efficacy outcomes will be maintained after cessation of the intervention.

Specific Aim 3: To determine the cost-effectiveness at 12-months of CHW and AE-C intervention delivery, and additional costs or savings related to asthma exacerbations at 12- and 24-months.

Specific Aim 4: To assess the efficacy of the integrated CHW home asthma intervention relative to clinic-based AE-C education, as demonstrated by asthma control, among those experiencing depression, stress, and/or post-traumatic stress disorder (PTSD). We hypothesize that among those living with depression, stress, and/or PTSD, the CHW intervention will be significantly more effective in achieving and maintaining asthma control than the AE-C education intervention.

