9.0 Data Analysis

All analyses will be performed by the investigators and analysts in the Institute for Health Research and Policy using SAS version 9.4. We will compare key population descriptors in the two treatment groups as patient recruitment progresses (at N=100 and N=150) to ensure that the randomization process is achieving reasonable balance, being careful to protect operational staff from bias. Basic summary statistics will be calculated for outcome variables and covariates. Continuous variables will be assessed for normality using Q-Q plots and compared using 2-sample t-tests. If distributions are sufficiently non-normal, then a suitable transformation or non-parametric test will be used. Categorical variables will be compared using chi-square tests. Significance tests will be two-sided at level $\alpha=0.05$.

Specific Aim 1: To assess the efficacy of the integrated CHW home asthma intervention relative to the AE-C intervention at 12-months post-randomization as demonstrated by asthma control. This study will employ two primary measures of asthma control: number of days with activity limitation over the previous 14 days and the Asthma Control Test/childhood Asthma Control Test (ACT/cACT). The mean total number of days with activity limitation over the previous 14-day period will be assessed at 12-months between the two treatment arms using the two-sample t-test or Mann-Whitney test. If the mean days with activity limitation in the intervention arm is at least 30% lower than that of the AE-C arm and $p < 0.05$, we will conclude that the CHW intervention is more effective. The ACT/cACT will be analyzed using similar methods; a MID of 0.2 will be used to determine intervention efficacy. Linear mixed models will

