Specific Aim 2: To assess maintenance of intervention efficacy, at 18 and 24 months after randomization. The asthma control measures will be compared between the two treatment groups at 18- and 24-months post-randomization as described above for Specific Aim 1. An indicator variable, to be named "Phase", will be added to the models to allow distinction between the time during intervention periods. The model will be: $Y_{it} = \beta_0 + \beta_1 Time_{ij} + \beta_2 Tx_i + \beta_3 (Tx_i * Time_{ij}) + \gamma_1 Phase_j * (Time_{ij} - 12) + \gamma_2 Tx_i * Phase_j * (Time_{ij} - 12) + \epsilon_{ij}$. We will conclude that any intervention effect is sustained if the slope for $\gamma_2 Time$ after 12-months continues to be positive in the CHW arm.

Specific Aim 3 compares the costs and cost effectiveness of the interventions. The analysis will be conducted from the societal perspective, including the costs borne by the program, individual participant and family, and healthcare system. 1) Cost and resource use information will be collected for the program, participant, and healthcare utilization. 2) Efficacy will be measured as asthma control as described for Specific Aim 1. 3) Cost effectiveness will be evaluated by combining the mean total cost per participant with change in asthma control. We will calculate the ICER for the CHW home intervention compared to AE-C services, such that $ICER_t = (C_1 - C_0) / (E_{1t} - E_{0t})$, where C is cost and E is effectiveness. Subscript 1 denotes CHW home intervention and subscript 0 denotes usual asthma care. t denotes the time period: 12 months, 18 months and 24 months. 95% confidence intervals for the ICERs will be calculated to evaluate the uncertainty in these results. 4) We will conduct one-way and multi-way sensitivity analyses for the key parameters to evaluate whether the ICERs are sensitive to plausible changes in their values. The sensitivity analysis is a check on the robustness and will determine the key parameters impacting the ICERs.

Specific Aim 4: To assess the efficacy of the integrated CHW home asthma intervention among those experiencing depression, stress, and/or PTSD. Interaction terms between treatment indicators for depression, stress, and PTSD will be examined to test for heterogeneity of treatment effects.

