12.0 Statistical Considerations

Statistical analysis is described in Section 9.0. The sample size for the study was determined to allow assessment of the relative efficacy of the proposed interventions with respect to asthma control. While a strong clinical definition of asthma control has been in place for some time, there is no gold standard for assessing asthma control. The Asthma Control Questionnaire (ACQ) has been validated in diverse, large samples but currently there is an absence of substantive data on this test (data such as variability and reasonable effect sizes within this target population) upon which statistical power and sample size estimates can be based. Therefore we have conducted two calculations to ensure adequate power. Using the ACQ, a sample size of 100 per group (total N=200) had power 0.87 to detect the minimally important difference (MID) of 0.5 established for this test.¹⁴ We performed a separate power calculation using number of days with activity limitation (over the past 14-days) as Zeiger et al.⁴² found "activity limitation" to be a strong determinant of the composite asthma control score. In a multi-site inner-city (including Chicago) randomized trial of a home CHW asthma intervention, Morgan et al. reported activity limitations over the previous 14 day period.⁴³ Based on their data, we hypothesize a mean of 3.9 "activity limitation" days at baseline in both groups (SE 0.22) and, in the AE-C comparison group, a mean at 12 months of 2.84 days (SE 0.10). We anticipate the proposed CHW intervention will be more potent than that tested by Morgan et al. because it involves a higher dose and more physician involvement. Within the proposed CHW home intervention group, we anticipate a mean of 2 "activity limitation" days over a 14-day period at 12 months (SE 0.10), representing a 30% reduction from the AE-C comparison group (and 50% reduction from the baseline mean). Further assuming an attrition rate of 15% and 80% power, the standard two-group t-test for comparing means (at 12 months) requires a sample size of about 111 per group, for a total of 223 participants. Analyses to examine heterogeneity of treatment effects by age, race, or other groups have more limited power but results will be considered suggestive for further research.

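### Aim 4 hypothesises a CHW benefit among families with depression, stress and/or PTSD, but the only analysis stated is an interaction test, which answers a different question

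*Combined protocol and SAP*

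**What the plan says.** Section 3.0, Specific Aim 4, states a directional hypothesis inside one group: "among those living with depression, stress, and/or PTSD, the CHW intervention will be significantly more effective in achieving and maintaining asthma control" than AE-C education. Section 9.0 opens the Aim 4 paragraph with the same objective, "To assess the efficacy of the integrated CHW home asthma intervention among those experiencing depression, stress, and/or PTSD". The one analysis sentence that follows is "Interaction terms between treatment indicators for depression, stress, and PTSD will be examined to test for heterogeneity of treatment effects". A word seems to be missing after 'treatment', but the sense is treatment-by-condition interactions.

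Sections 9.0 and 12.0 give no treatment contrast within the affected group, no confidence interval and no decision rule for Aim 4. Aims 1 and 2 each have an explicit rule for drawing a conclusion. Section 12.0 does say that heterogeneity analyses by age, race or other groups have more limited power and will be treated as suggestive.

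The Aim 4 paragraph also leaves the affected group undefined. It gives no instrument, cut-off or time point, does not say whether child or caregiver status counts, and does not say how the 'and/or' is combined. Section 6.8.4 has call-back thresholds for the PHQ-9, the PTSD checklist and the CDI2, but none for the Perceived Stress Scale.

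**The concern.** The hypothesis is about a simple effect: CHW versus AE-C among the affected. The stated test is about a difference of effects: affected versus unaffected. Neither result implies the other, so the planned test can be null when the hypothesis is true and significant when it is false.

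Aim 4 bears on one of the three features that set this CHW programme apart, its system for psychosocial barriers (section 1.0). As written, the plan does not commit to reporting the estimate that would answer it.

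Timing matters too. The CHW arm is designed to act on psychosocial barriers, so a score taken after randomization could itself be changed by treatment. Grouping families on such a score would no longer compare randomized groups.

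**Working it through.** **1. The two questions side by side.** Let D1 be the CHW minus AE-C difference among the affected and D0 the same difference among the unaffected. The hypothesis concerns D1. The interaction tests D1 − D0.
- Uniform benefit (D1 = D0 ≠ 0): hypothesis true, interaction zero.
- Benefit only in the unaffected (D1 = 0, D0 ≠ 0): hypothesis false, interaction non-zero.
- Benefit only in the affected (D1 ≠ 0, D0 = 0): hypothesis true, interaction non-zero.

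This step needs no numbers and holds for any SD.

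**2. Inputs for an illustration (section 12.0 unless noted).** AE-C: "a mean at 12 months of 2.84 days (SE 0.10"). CHW: mean 2 days. Difference: 2.84 − 2 = 0.84 days. Power 80%, attrition 15%, 223 participants; two-sided 0.05 (section 9.0). The documents give SEs but no SD, and not the sample size behind the SEs.

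**3. The plan's own sample size.** It cannot be reproduced directly. Reading 0.10 as the SD gives 1 per arm. Reading it as the SE at 95 per arm (SD about 0.97) gives 22 per arm. Working backwards:
- evaluable per arm = 223 × 0.85 / 2 = 94.8
- SD = 0.84 / [(1.96 + 0.84) × √(2/94.8)] ≈ 2.06, where the 0.84 in the bracket is the normal quantile for 80% power
- check: SE = 2.06 × √(2/94.8) = 0.299, and the two-sample t-test has 79.7% power

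So 223 is consistent with an SD of about 2.06, which is inferred and not stated.

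**4. Within-group and interaction power.** With share p affected, a = 94.8p and b = 94.8(1 − p) per arm:
- SE within = 2.06 × √(2/a)
- SE interaction = 2.06 × √(2/a + 2/b), which is SE within / √(1 − p)

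The range of p is assumed. The only prevalence in the documents is from the earlier pilot: "59% of caregivers and 68% of teens reported signs of depression". That covers depression alone, so a group defined by any of the three conditions could be larger.

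| p | a, b per arm | SE within | SE interaction | Power within, D1 = 0.84 | Power interaction, D1 = 0.84 and D0 = 0 |
|---|---|---|---|---|---|
| 30% | 28.4, 66.3 | 0.546 | 0.653 | 33% | 25% |
| 50% | 47.4, 47.4 | 0.423 | 0.599 | 50% | 29% |
| 59% | 55.9, 38.9 | 0.390 | 0.608 | 57% | 28% |
| 68% | 64.4, 30.3 | 0.363 | 0.642 | 63% | 26% |
| 80% | 75.8, 19.0 | 0.335 | 0.748 | 70% | 20% |
| 90% | 85.3, 9.5 | 0.315 | 0.998 | 75% | 13% |

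If the benefit is 0.84 days in both groups, within-group power is unchanged and the interaction rejects 5% of the time, its null rate. If only the unaffected benefit by 0.84 days, the within-group test rejects 5% of the time and the interaction has the power in the last column.

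**5. Do the written models contain the contrast?** No. The Aim 1 model has Time, Tx and Tx×Time. The Aim 2 model adds Phase terms after month 12. Neither has a psychosocial term.

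**The case against.** The best defence is that section 9.0 restates the objective as efficacy among the affected just before the interaction sentence. A model with a treatment-by-condition interaction also holds the within-group effect as a linear combination, so an analyst could derive it without new data. Testing an interaction is good practice for a subgroup aim, and section 12.0 already calls heterogeneity results low-powered and suggestive; its 'other groups' plausibly covers Aim 4.

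Most of this stands, and it limits the point to an unnamed contrast. It does not remove the point: the plan does not commit to that contrast, and the caveat about interactions does not supply an estimate among the affected.

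A reader might infer more than the documents support:
- **That Aim 4 cannot confirm its hypothesis, or that a null interaction would be reported as failure.** Aim 4 has no decision rule, so the text says neither.
- **That psychosocial status will be measured after randomization.** The Aim 4 sentence is silent on timing, and the visit marks in the assessment table are not legible in the text available. The timing needs stating; misuse is not shown.
- **That using three indicators is an error.** If most families meet at least one condition, a combined group would nearly repeat Aim 1, and separate conditions may be preferable if mechanisms differ.
- **That the power figures are the plan's own.** They rest on an inferred SD and an assumed prevalence, and cover activity-limitation days only, although ACT/cACT is also a primary measure.

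**Conclusion.** The mismatch is real, in a non-primary aim. The hypothesis is an effect among the affected, the stated test is a difference between affected and unaffected, and the within-group estimate is not specified in section 9.0 or 12.0. That conclusion is logical and rests on no assumed number.

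The illustrative size is about 33% to 75% power for the within-group contrast. For the interaction it is about 13% to 29% if the whole effect lies in the affected, and 5% if the effect is uniform. These figures assume an SD of 2.06, 94.8 evaluable per arm and 30% to 90% affected. Within-group power is modest across that range, so the estimate and its interval should carry the result rather than the p-value.

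**What to change.** Before analysis, amend the Aim 4 paragraph of section 9.0 as follows.
- **Define the affected group at baseline.** State the instruments and cut-offs (including one for stress), and whether child status, caregiver status or either counts. The sponsor chooses whether the combined group or the three conditions separately lead; the other is reported as supportive.
- **Extend the Aim 1 and Aim 2 models.** Add the indicator (Ind) and its interactions with treatment and time, including the Phase terms.
- **Name the Aim 4 result.** Report the CHW minus AE-C difference among the affected, with 95% CI, at 12, 18 and 24 months, because the hypothesis covers both achieving and maintaining control. With Time in months, and δ1, δ2, δ3 the coefficients of Ind×Tx, Ind×Tx×Time and Ind×Tx×Phase×(Time − 12), the contrast at month t is β2 + tβ3 + δ1 + tδ2, plus (t − 12)(γ2 + δ3) for t above 12. Each visit needs one estimate statement.
- **Keep the interactions** as the test of heterogeneity, labelled suggestive in line with section 12.0.

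The cost is a few model terms and contrasts, with no added participants, visits or instruments. The downsides are modest within-group power and the need for careful wording: an effect within the subgroup must not be reported as a difference between subgroups. This is a cheap improvement.

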10.0 Quality Control and Quality Assurance

Intervention fidelity procedures are described in Section 6.6. The MRC will develop quality assurance checks that will be implemented at the time data are entered as an assurance of data accuracy. Erroneous and/or inconsistent values will prompt generation of an entry to a query report that will be developed for this study. Query reports will be generated weekly and distributed to study staff for resolution. Once generated, a query will remain part of the weekly report until it is resolved.

11.0 Data and Safety Monitoring

11.1. Data Safety Monitoring Board

A Data Safety Monitoring Board (DSMB) has been created to provide oversight for the proposed trial. We have a 6 member DSMB. At its first meeting, the DSMB elected one of the members to serve as the Chair and another to serve as Executive Secretary. DSMB members and their expertise are as follows:

- *[name]; Medical Psychologist, Ann & Robert H. Lurie Children's Hospital of Chicago (health psychologist)*
- *[name]: University of Illinois at the School of Public Health (Biostatistician)*
- *[name], Associate Professor, Rush University Medical Center (behavioral intervention researcher and health psychologist)*
- *[name], JD; Chief Medical Officer, Mile Square Health Center (federally-qualified health center administrator)*
- *[name], Mile Square Health Center (community pediatrician)*
- *[name], Medical Director, Public Health and Safety Division, Department of Public Health, City of Chicago, Illinois (local health expert)*

The data management team will report directly to the DSMB chairperson at their request or every 12 months. The DSMB will make an affirmative decision at each meeting whether to continue or terminate the study. Early termination is an option for the DSMB, particularly if there are serious concerns about patient safety or there is evidence of futility or sufficient evidence of efficacy; decisions regarding early termination will be made by the DSMB. No interim analyses of outcomes for efficacy or futility are planned. In general, the DSMB will be provided data grouped by treatment without identified treatment groups (i.e., masked to treatment assignment). If the DSMB requests, for the purpose of competent deliberation, to see the treatment assignments (by group or individual), these will be provided by the lead biostatistician. The investigators will remain masked to the treatment assignments of individual patients unless it is judged that it is in the best interests of an individual patient.

11.2. Adverse events (AEs) and Unanticipated Problems (UPs)

The Data Coordinating Center (DCC) will work with study staff to monitor any AEs and UPs that occur among participants of the proposed study. The two primary risks are: 1) confidentiality (protection of data, especially sensitive data collected in home); and 2) mental health risk (not

from the intervention, but assessments query for risks of harm to self or others). Confidentiality risks are managed by the procedures described in Data Acquisition and Maintenance Section. Mental health risks are managed as indicated on the Mental Health Protocol (See section 6.8.4). Adverse events will be reported immediately to the Safety Officer ([name]). When indicated, the Safety Officer will inform the Principal Investigator, IRB, DSMB, Compliance Office, and/or NIH. Action to protect participant safety and privacy will be taken. Serious and non-serious AEs will be reported by the Principal Investigator to the IRB and NHLBI within 14 calendar days of initial receipt of information. UPs that are not serious AEs will be reported by the Principal Investigator to the IRB and NHLBI within 14 calendar days of when the investigator becomes aware of the problem.

11.3. Data Management

Data management for this project will be provided by the Methodology Research Core (MRC) in the Institute for Health Research and Policy at UIC. The MRC also serves as the Design and Analysis Core of the University of Illinois at Chicago Center for Clinical and Translational Science (CCTS) which is supported by NIH funding through a Clinical and Translational Science Award as well as strong institutional commitment. The MRC has extensive experience in the acquisition, maintenance, and analysis of both large and small clinical trial databases. It is directed by [name] who is a co-investigator on this proposal. The MRC faculty and staff are located in same offices as the other UIC investigators. Specific activities of the MRC include: collaborating with the study team to develop a comprehensive, yet efficient, set of case report forms to capture participant data, developing web and direct data capture systems, processing data, implementing and maintaining an effective study database and its associated query system, maintaining a computer environment sophisticated enough to efficiently, effectively, and securely manage the study database, and developing regular reports as to the accuracy and completeness of the study database, participant follow-up, and intervention delivery. The MRC is part of the research team which supports the ready exchange of any needed resources. The MRC will also implement the randomization processes. Access to randomization assignment data will be limited to pertinent MRC staff (who have no interaction with participants) and designated study personnel who are responsible for ensuring participant safety.

